2.9 Safety analyses

All safety analyses will be based on the SAF set.

2.9.1 Adverse events

Treatment emergent adverse events (events started after the first dose of secukinumab study treatment or events present prior to the first dose of secukinumab study treatment but increased in severity) will be summarized by preferred term up to 28 weeks after the first dose..

AEs will be summarized by presenting, for each treatment group, the number and percentage of patients having any AE, having an AE in each primary system organ class (SOC) and having each individual AE (preferred term).

Summaries will also be presented for AEs by severity and for secukinumab study treatment (with and without life-style intervention) related AEs. If a patient reported more than one adverse event with the same preferred term, the adverse event with the greatest severity will be presented. If a patient reported more than one adverse event within the same primary SOC, the patient will be counted only once with the greatest severity at the SOC level, where applicable. Furthermore, a listing of all adverse events, including SAE, will be provided. SAEs will be summarized.

Separate summaries will be provided for death, SAE, other significant AEs leading to secukinumab study treatment (with and without life-style intervention) discontinuation and AEs leading to dose adjustment (including secukinumab study treatment discontinuation).

Deaths occurring after signing of informed consent and prior to the start of the core study will be presented in the listing.

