3.1 Study design

Figure 3-1 Study design

[figure not shown]

Fig. 3-1: Study Design: R Randomization, *During the extension period lifestyle intervention can be continued by patients who have been in arm B during the core study or it can be started by patients who have been in arm A. Participation in the lifestyle intervention during the extension period is **not** mandatory. †Participation in the extension period itself is mandatory. Psoriasis treatment during the extension period can be chosen freely by the Investigator. No study drug is supplied during the extension period.

This study is designed as a randomized, open-label, parallel-group, active comparator-controlled trial with two treatment arms. The design is shown in Figure 3-1.

Core study: After providing informed consent patients will be screened for eligibility for a period of 1-4 weeks prior to inclusion into the study. If eligible, patients will then be randomized to one of the two treatment arms, which are the following:

- **Arm A:** Patients in arm A receive a regular induction followed by 4-weekly maintenance treatment with Secukinumab 300 mg s.c. until week 28, where they complete the core study. The last Secukinumab injection is performed at week 24.
- **Arm B:** Patients in arm B receive a regular induction followed by 4-weekly maintenance treatment with Secukinumab 300 mg s.c. until week 28. The last Secukinumab injection is performed at week 24. **In addition to Secukinumab treatment patients in arm B participate in a lifestyle intervention program.**

A biomarker sub-study will be conducted during the core study in a subgroup of 100 patients (50 from each treatment arm).

The core study ends at week 28.

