If a subject re-screens for the study, then the subject must sign a new ICF and be issued a new subject number prior to any screening assessment being conducted for the subject under the new screening subject number. For all subjects, the investigator/qualified site staff will record if the subject was re-screened on the re-screening eCRF and any applicable screening numbers the subject was issued prior to the current screening number. The date of the new informed consent signature must be entered on the Informed Consent eCRF to correspond to the new screening subject number. For re-screening, all screening assessments must be performed per protocol, except for the tuberculosis (TB) work up if applicable, if performed not more than 12 weeks before randomization.

Table 6-1 Assessment schedule

| Visit Number | 1 | 2 | 3 | 4 | 5 | 6 | 7 | 8 | 9 | 10 | 11 | 12 | E1 | E2 | E3 | US V ⁴ |
|--|-------------|---|---|----|----|----|----|----|-----|-----|-----|-----|-----|-----|-----|-------------------|
| Week | -4 - -1 | 0 | 1 | 2 | 3 | 4 | 8 | 12 | 16 | 20 | 24 | 28 | 36 | 44 | 56 | |
| Day | -28 - -7 | 1 | 8 | 15 | 22 | 29 | 57 | 85 | 113 | 141 | 169 | 197 | 253 | 309 | 393 | |
| Obtain informed consent | X | | | | | | | | | | | | | | | |
| Obtain informed consent for biomarker sub-study ⁹ | X | | | | | | | | | | | | | | | |
| Demographics | X | | | | | | | | | | | | | | | |
| Inclusion/exclusion criteria ¹ | X | X | | | | | | | | | | | | | | |
| Smoking history | X | | | | | | | | | | | X | | | X | |
| Medical history and prior medications | X | | | | | | | | | | | | | | | |
| Cardiovascular/metabolic medical history | X | | | | | | | | | | | | | | | |
| Concomitant medications | X | X | X | X | X | X | X | X | X | X | X | X | X | X | X | X |
| Physical examination | S | S | | | | | | | S | | | S | | | S | S ⁵ |
| Height | X | | | | | | | | | | | | | | | |
| Weight | X | X | X | X | X | X | X | X | X | X | X | X | X | X | X | X ⁵ |
| Vital signs | X | X | X | X | X | X | X | X | X | X | X | X | X | X | X | X ⁵ |
| Waist and hip circumference | X | X | X | X | X | X | X | X | X | X | X | X | X | X | X | |
| Routine Laboratory [‡] | C | C | | C | | C | C | C | C | C | C | C | C | C | C | C ⁵ |
| Fasting Laboratory [‡] | C | C | | | | | C | | C | | | C | C | C | C | C ⁵ |
| QuantIFERON test ² | C | | | | | | | | | | | | | | | C ⁵ |
| Serum pregnancy test ³ | C | | | | | | | | | | | C | | | C | C ⁵ |
| Local pregnancy test | | X | | | | | | | | | | | | | | C ⁵ |

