9.5.2 Safety variables

9.5.2.1 Adverse events

Treatment emergent adverse events (events started after the first dose of study treatment or events present prior to the first dose of study treatment but increased in severity) will be summarized by preferred term up to 12 weeks (84 days) after the last dose. Non-treatment-emergent AEs will be listed in a listing but not summarized.

Adverse events will be summarized by presenting, for each treatment group, the number and percentage of patients having any AE, having an AE in each primary system organ class and having each individual AE (preferred term). Summaries will also be presented for AEs by severity and for study treatment related AEs. If a patient reported more than one adverse event with the same preferred term, the adverse event with the greatest severity will be presented. If a patient reported more than one adverse event within the same primary system organ class, the

patient will be counted only once with the greatest severity at the system organ class level, where applicable. Furthermore, a listing of all adverse events, including SAE, will be provided.

Serious adverse events will also be summarized.

Separate summaries will be provided for death, serious adverse event, other significant adverse events leading to discontinuation and adverse events leading to dose adjustment (including study treatment discontinuation).

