Based on these assumptions 342 patients per arm would provide a power of 90 % at a two-sided alpha of 0.05 to demonstrate that the percentage of PASI90 responders at week 28 is higher in the Secukinumab combined with lifestyle intervention arm compared to the Secukinumab alone arm. In case the true effect size would only be 7.5 %, this sample size would still provide a power of 75 %. To compensate for some expected drop out and/or premature discontinuations, 380 patients per arm are planned to be recruited for this study.

4 Change to protocol specified analyses

Below mentioned changes to the analysis described in Section 9 of the protocol version 02 are planned.

- i. Separate analyses will be performed for subjects with fasting and non-fasting status for fasting plasma glucose, fructosamine, and HbA1c in secondary analyses
- ii. Separate analyses will be performed for subjects with fasting and non-fasting status for all the biomarkers in biomarker sub-study
- iii. Additional analysis proposed for stratification of the analysis for PASI 75, PASI 90, PASI 100 and all study biomarkers by the groups “patients achieving weight loss < 5%”, “patients achieving weight loss $\geq 5\%$ - < 10%” and “patients achieving weight loss $\geq 10\%$ ” in each treatment arm.

5 Appendix

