5.2 Visit windows and mapping of visits

Visit-windows will be used for biomarker sub-study data that is summarized by visit; they are based on the study assessment schedule and comprise a set of days around the nominal visit day. For any assessment there will be a visit window to cover the complete range of days within the study. So, the overlapping visit window period will be used for the analyses, as mentioned below in [Table 5-1](#).

Table 5-1 Assessment windows for scheduled visits

Analysis Visit	Week	Scheduled Day	Visit Window
Baseline	0	1	-28 days to Day 1
Week 16	16	113	Day 99-127
Week 28	28	197	Day 183-225

Clinical Development

CAIN457A/METABOLYX

CAIN457ADE08

A randomized, multicenter 28 week study to compare the efficacy and safety of combining Cosentyx (Secukinumab) (4 weekly, 300 mg s.c.) with a lifestyle intervention to Cosentyx therapy alone in adult patients with moderate to severe plaque type psoriasis and concomitant metabolic syndrome, followed by a 28 week extension period

Extension Period Statistical Analysis Plan (SAP)

Document type:	SAP Documentation
Document status:	Addendum 1.0
Release date:	19-Sep-2022
Number of pages:	21

Property of Novartis
Confidential
May not be used, divulged, published or otherwise disclosed
without the consent of Novartis

Template Version 4.0, Effective from 23-Apr-2021

Document History – Changes compared to previous final version of SAP

Date	Time point	Reason for update	Outcome for update	Section and title impacted (Current)
27-Jul-2022	Prior to DB lock	Creation of final version	N/A - First version	NA
19-Sep-2022	After Final DB lock	Creation of Addendum version 1.0	Text modified in section 2.6.1	2.6.1

Table of contents

Table of contents	3
List of abbreviations	5
1 Introduction	6
1.1 Study design.....	6
1.2 Study objectives and endpoints	7
2 Statistical methods.....	8
2.1 Data analysis general information	8
2.1.1 General definitions	8
2.2 Analysis sets	8
2.3 Patient disposition, demographics, and other characteristics	8
2.3.1 Patient disposition	8
2.3.2 Demographics and other characteristics.....	9
2.4 Treatments (study treatment, rescue medication, concomitant therapies, compliance).....	9
2.4.1 Study treatment / compliance.....	9
2.4.2 Study Compliance	9
2.4.3 Concomitant and post therapies	10
2.5 Analysis supporting study objective(s).....	10
2.5.1 Endpoint(s).....	10
2.5.2 Statistical hypothesis, model, and method of analysis.....	11

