2.6.1 Adverse events (AEs)

Treatment-emergent adverse events (events started after the administration of first dose of secukinumab in the Core phase or events present prior to the initiation of Core phase but increased in severity) will be summarized by preferred term. Additionally, AE(s) reported up to 84 days post Week 24 (i.e., till Week 36) will be considered as TEAEs.

All the AEs reported Week 36 onwards will be listed & summarized by preferred term up to last study assessment i.e., Week 56.

If a patient reports more than one AE with the same preferred term, the AE with the greatest severity will be presented. If a patient reports more than one AE within the same primary SOC, the patient will be counted only once with the greatest severity at the SOC level, where applicable. Furthermore, a listing of all AEs, including SAE, will be provided. SAEs will be summarized.

In the extension period, the treating physician is free to choose suitable psoriasis therapy for each patient. Summaries will be presented for AEs by severity and for chosen therapy (marketed secukinumab, Novartis or Non-Novartis products) related AEs.

Separate summaries will be provided for death, SAE, other significant AEs leading to discontinuation of study grouped by therapy chosen by treating physician.

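### Neither SAP ends the treatment-emergent AE window at the patient's own last dose plus 84 days, as the protocol does, and neither declares the change

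*SAP*

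**What the plan says.** Protocol 9.5.2.1 says that TEAEs "will be summarized by preferred term up to 12 weeks (84 days) after the last dose". It adds: "Non-treatment-emergent AEs will be listed in a listing but not summarized". The end of the window therefore decides whether an event reaches a summary table, and it is set by each patient's own last dose.

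Core SAP 2.9.1 says that TEAEs "will be summarized by preferred term up to 28 weeks after the first dose". The length changes, and so does the anchor, from last dose to first dose. No reason is given.

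Core SAP section 4 opens: "Below mentioned changes to the analysis described in Section 9 of the protocol version 02 are planned". Three items follow: a fasting split for the glucose markers, a fasting split for the sub-study biomarkers, and the weight-loss strata. None concerns adverse events.

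Extension SAP 2.6.1 says: "AE(s) reported up to 84 days post Week 24 (i.e., till Week 36) will be considered as TEAEs". This uses the protocol's 84 days but counts them from the scheduled last dose rather than the actual one. Section 4 of that SAP mentions added safety analyses in general terms and says nothing about the TEAE window.

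The extension SAP's document history records that text in 2.6.1 was modified at a time point given as "After Final DB lock". It does not say which text.

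**The concern.** A TEAE window should follow exposure. The protocol's does, and its 84 days is not a stray figure: the SAE reporting rules in Protocol 7.2.2 also use 12 weeks after the last secukinumab administration. A cut fixed to the calendar departs from exposure in two directions.

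- A patient who completes dosing has most of the post-dose period left out of the core TEAE summary.
- A patient who stops early has events counted as treatment-emergent long after the protocol would stop counting. Protocol 5.6.2 and footnote g of Table 5-1 lift all restrictions on other psoriasis treatment, biologics included, once secukinumab is stopped, while study visits continue. Events on the replacement drug can then enter the secukinumab TEAE tables.

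The core and later analyses go into separate reports (Protocol 9.7). Their TEAE rates will rest on different windows, at least one of which will not be the protocol's, with no explanation in either SAP. Nor is a comparison of the arms over the protocol window clearly planned: core 2.9.1 presents AEs by treatment group but stops at Week 28, while extension 2.6.1 does not say that its TEAE summary is by arm and groups several summaries by the therapy the physician chose.

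**Working it through.** **Inputs.** Last scheduled dose: "The last Secukinumab injection is performed at week 24" (Protocol 3.1). Scheduled days in Protocol Table 6-1, Weeks 20 to 56: "141 | 169 | 197 | 253 | 309 | 393", so Week 24 is Day 169, Week 28 is Day 197 and Week 36 is Day 253. The general rule is day = 7 × week + 1. The windows are those of Protocol 9.5.2.1, core SAP 2.9.1 and extension SAP 2.6.1.

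**The plan's own figure.** Day 169 + 84 = Day 253, and (253 − 1)/7 = 36. The extension SAP's Week 36 is reproduced for a patient last dosed on schedule at Week 24.

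**Patient dosed through Week 24.**
- Core window ends at Day 1 + 28 × 7 = Day 197.
- Post-dose days covered: 197 − 169 = 28 of 84 (33%).
- Post-dose days left out: 253 − 197 = 56.
- Whole protocol window: 253 − 1 = 252 days. The core SAP keeps 196/252 = 78% and omits 56/252 = 22%.

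**Window end by last dose** (protocol end = last-dose week + 12):

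| Last dose (week) | Protocol end (week) | Core SAP end (week) | Core minus protocol (weeks) | Extension SAP end (week) | Extension minus protocol (weeks) |
|---|---|---|---|---|---|
| 0 | 12 | 28 | +16 | 36 | +24 |
| 4 | 16 | 28 | +12 | 36 | +20 |
| 8 | 20 | 28 | +8 | 36 | +16 |
| 12 | 24 | 28 | +4 | 36 | +12 |
| 16 | 28 | 28 | 0 | 36 | +8 |
| 20 | 32 | 28 | −4 | 36 | +4 |
| 24 | 36 | 28 | −8 | 36 | 0 |

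The core SAP agrees with the protocol only for a last dose at Week 16. It is shorter for later last doses and longer for earlier ones. The extension SAP agrees only for a last dose at Week 24 and is longer for every earlier stopper. After a last dose at Week 4, the core SAP counts 28 − 4 = 24 weeks post-dose and the extension SAP 36 − 4 = 32 weeks, against 12 in the protocol.

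**What cannot be computed.** The documents do not say how many patients are expected to stop secukinumab early, or when. The increase from 342 to 380 per arm (38/380 = 10%) is a combined allowance for dropout and premature discontinuation, without timing. The effect on TEAE rates therefore cannot be sized.

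**The case against.** A Week 28 cut in the core report has a sound rationale. The first analysis is planned once everyone has completed the core study (Protocol 9.7). The last patients will then have just reached Week 28, and follow-up from Week 28 to Week 36 will be incomplete. After Week 28 lifestyle intervention is open to both arms and psoriasis therapy is free, so a core-period cut also protects the randomized comparison. This stands. It argues for keeping a core cut, but also for declaring it, and core SAP section 4 does not.

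The later events are not lost. Extension SAP 2.6.1 counts events to Week 36 as TEAEs, and extension SAP 2.6 reports AEs cumulatively to Week 56. Core SAP 2.9.1 also lists all AEs, and its separate summaries of deaths, SAEs and discontinuations state no 28-week limit. This stands too. A reader might infer that the trial discards most post-dose safety data, and that inference would be wrong: the shortfall is in one of two planned reports.

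A patient in the combination arm may stop secukinumab and continue the lifestyle program, since Protocol 5.6.2 says stopping one should not by itself stop the other. A window tied only to secukinumab would drop later events from the summary, although lifestyle is the randomized contrast. This is a fair point. It is met by showing all AEs to Week 28 by arm alongside the TEAE table.

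A reader might also infer from the document history that the TEAE window was rewritten after database lock. The documents do not show that. They show only that some text in 2.6.1, a section covering several topics, was modified then; the previous wording is not given, and the timing is disclosed in the dated history.

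**Conclusion.** The point holds as a departure from the protocol's stated rule in both SAPs, undeclared in either section 4. The core report leaves out 56 of the 84 post-dose days for a patient dosed through Week 24. For that patient the extension SAP restores the protocol window exactly. For early stoppers both SAPs overrun, by up to 16 weeks (core) and 24 weeks (extension), into a period when replacement psoriasis therapy is unrestricted. No summary by arm over the protocol window is clearly planned in either report.

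The importance is moderate. AE summaries are descriptive, the primary endpoint is untouched, and the events are collected. The figures assume visits and doses on the scheduled days. The effect on rates depends on an unstated number of early stoppers.

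**What to change.** 1. **Extension SAP 2.6.1:** define TEAEs as onset or worsening from first dose to the patient's own last study secukinumab dose plus 84 days. Specify study drug, because marketed secukinumab may be used in the extension. Present the summary by randomized arm, split at Week 28.
2. **Core SAP 2.9.1:** keep the Week 28 core-period cut, but end the TEAE window at the earlier of Week 28 and last dose plus 84 days. Show all AEs to Week 28 by arm in a separate table, so that events during continued lifestyle intervention are not dropped.
3. **Core SAP section 4:** declare the core-period cut, give the reason, and point to the final report for the full protocol window.

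The cost is SAP wording and a re-run of the AE tables on data already collected; no visit or data item is added. An amendment made now to the extension SAP would post-date the final lock in its document history and should be labelled accordingly.

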2.9.2 Laboratory data

The summary of laboratory evaluations will be presented for three groups of laboratory tests (hematology, clinical chemistry and urinalysis). All the laboratory parameters and biomarkers with values below and above the limit of quantification (LOQ) will be reported as LOQ/2. Descriptive summary statistics for the change from Baseline to each study visit will be presented.

These descriptive summaries will be presented by test group, laboratory test and treatment group. Change from Baseline will only be summarized for patients with both Baseline and Post-Baseline assessments.

Change from baseline = post-baseline value – baseline value

For each parameter, the maximum change from Baseline within each study period will be analyzed analogously.

Below mentioned laboratory parameters will be descriptively summarized. Frequencies and percentages will be presented for patients with clinically notable laboratory value, for below mentioned selected lab parameters:

Clinically notable laboratory values

Liver Function and Related Variables

- ALT (SGPT): $> 3 \times$ Upper Limit of Normal (ULN)
- AST (SGOT): $> 3 \times$ ULN
- Total bilirubin: $> 1.5 \times$ ULN
- Alkaline phosphatase: $> 2 \times$ ULN

Renal Function and Electrolyte Variables

- Creatinine (serum): $> 1.5 \times$ ULN

Hematology Variables

- Hemoglobin: ≥ 20 g/dL decrease from baseline
- Platelet count: $<$ Lower Limit of Normal (LLN)
- White blood cell count: $< 0.8 \times$ LLN
- Neutrophils: $< 0.9 \times$ LLN
- Eosinophils: $> 1.1 \times$ ULN
- Lymphocytes: $> 1.1 \times$ ULN

Clinically significant abnormal laboratory values will also be summarized for the following parameters of the biomarker sub-study: Adiponectin, leptin, insulin, HOMA-IR, proinsulin, IL-6, TNF-alpha, M30 assay, NT-proBNP. Only patients participating in the biomarker sub-study will be included.

